4.1.5 Multi-Site Research

All sites have the most current version of the protocol, consent document, and HIPAA authorization.

All required approvals (initial, continuing review and modifications) have been obtained at each site (including approval by the site's IRB of record).

All modifications have been communicated to sites and approved (including approval by the site' s IRB of record) before the modification is implemented.

All engaged participating sites will safeguard data, including secure transmission of data, as required by local information security policies.

All local site investigators will conduct the study in accordance with applicable federal regulations and local laws.

All non-compliance with the study protocol or applicable requirements will be reported in accordance with local policy.

Refer to Appendix C: Instructions for Multi-Site Studies.

5 PARTICIPANT SELECTION

5.1 Inclusion Criteria

To be included in this study, participants must meet the following criteria:

- 1. Age \geq 18 years of age.
- 2. Eligibility checklist before registration requires review of case by study surgeon or interventional pulmonologists to approve anatomic feasibility of an airway intervention.
- 3. For patients in Cohort B only. Patients are amenable to receive a palliative radiotherapy of 8 Gy x1 48±4 h prior to the I-PDT, as determined by the radiation oncologist.
- 4. Patients with an established pathologic diagnosis of small cell and/or non-small cell lung cancer or other malignancies causing airway obstruction > 25% requiring bronchoscopic intervention. Or inoperable malignancies not candidates for curative radiotherapy within the airway.
- 5. Have an ECOG Performance Status of \leq 3. Refer to Appendix A.
- 6. Have the following clinical laboratory values:

-Platelets \geq 100,000 cells/mm³ (SI units100 x 10⁹/L)

- 7. Participants of child-bearing potential must agree to use adequate contraceptive methods (e.g., hormonal or barrier method of birth control; abstinence) prior to study entry. Should a woman become pregnant or suspect she is pregnant while she or her partner is participating in this study, she should inform her treating physician immediately.
- 8. Participant must understand the investigational nature of this study and sign an Independent Ethics Committee/Institutional Review Board approved written informed consent form prior to receiving any study related procedure.

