4 METHODOLOGY

4.1 Study Design

This is a multi-center, multi-arm, Phase I (Cohort 0; data collection complete) to monitor the safety and Phase II study (Cohort A and Cohort B described below) to monitor the efficacy of EBUS-

TBN guided I-PDT and/or I-PDT and/or PDT in patients with malignant airway obstructions that are refractory to curative chemoradiation or, who are not candidates for curative chemoradiation. Participants will be treated on an outpatient or inpatient basis, and the treating physician will make this decision on a case-by-case basis.

Cohort 0 is closed to accrual and fulfilled the Phase 1 safety monitoring requirements. Cohort 0 provided the safety monitoring component for Cohort A of this Phase II study. Cohort 0 consisted of patients with the diagnosis of lung cancer that received porfimer sodium with EBUS I-PDT and participated in all of the study procedures except the Quality of Life Questionnaires and Six Minute Walk Test.

Cohort A (n=18, Phase II) consists of patients with a diagnosis of lung cancer or other malignancies causing airway obstruction or inoperable malignancies not candidates for curative radiotherapy within the airway; and that receive EBUS I-PDT and all of the study procedures. Subjects treated in Cohort 0 are considered the Phase I part of Cohort A.

Cohort B (n=39) will consist of patients with the diagnosis of lung cancer or other malignancies causing airway obstruction, or inoperable malignancies not candidates for curative radiotherapy within the airway. Subjects in Cohort B will receive the EBUS-guided I-PDT 48 ± 4 h after standard of care palliative radiotherapy of 8 Gy x1.

NOTE: Given the nature of this advanced airway procedure, only the physician performing the procedure will be the consenter for the procedure as well as for the study.

All participants will undergo the standard of care interventional bronchoscopy procedure with an attempt to treat and resolve the airway obstruction using conventional methods such as mechanical debulking, tumor ablation, and/or airway stenting. Airway stenting will be performed before or after I-PDT and/or PDT, as necessary. Curvilinear EBUS with Color Doppler will be used to guide the intra-tumor fiber insertion.

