5.2 Exclusion Criteria

Participants will be excluded from this study for the following:

- 1. Participants who have had curative radiotherapy to the target tumor within 4 weeks prior to the scheduled I-PDT and/or PDT.
- 2. Uncontrolled intercurrent illness including, but not limited to, ongoing or active infection, symptomatic congestive heart failure, unstable angina pectoris, cardiac arrhythmia, or psychiatric illness/social situations that would limit compliance with study requirements.
- 3. Pregnant or nursing female participants.
- 4. Co-existing ophthalmic disease likely to require slit-lamp examination within 14 days following I-PDT and/or PDT treatment.
- 5. Known hypersensitivity/allergy to porphyrin.
- 6. Patients who are not cleared by the anesthesiologist to undergo an advanced bronchoscopy procedure under general anesthesia.
- 7. Patients with target tumor invading into the lumen of the esophagus, confirmed by esophago-gastro-duodenoscopy (EGD) with endoscopic ultrasound.
- 8. Patients diagnosed with porphyria.
- 9. Unwilling or unable to follow protocol requirements.
- 10. Any condition which in the Investigator's opinion deems the participant an unsuitable candidate to receive I-PDT or PDT.

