6 TREATMENT PLAN

Dosing, Administration and Intervention

The following table summarizes the treatment plan for each study cohort.

Cohort	Participant disease	Treatment	Additional therapy or intervention
Cohort A	Cancer causing airway narrowing.	Participants will be treated with PDT or I- PDT using treatment planning developed by [name] and the treatment	

	Or Cancer is not a candidate for surgery or curative radiation therapy.	planning developed by a company (Simphotek Inc.).	
Cohort B	Cancer causing airway narrowing. Or Cancer is not a candidate for surgery or curative radiation therapy	Participants will be treated with PDT or I- PDT using treatment planning developed by [name].	Participants will receive one treatment of palliative radiotherapy two days before the PDT or I-PDT.

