12.1.3 Primary Phase II Efficacy Analysis

The primary endpoint for Cohort A and Cohort B is the proportion of complete responders (CR) and partial responders (PR) as measured by RECIST v1.1 at 12 ± 1 week after DOSIETM (Cohort A) and COMSOLTM guided I-PDT.

For Cohort A, we hypothesize that the objective tumor response for CR+PR will be at least 29%. We also want to investigate the impact of variation in optical properties, Photofrin® retention, and fiber location perturbation on the objective tumor response. The primary analysis will consist of a one-sided exact binomial test of H₀: π =0.05 versus H_a: π >0.05 at level α =0.05, where π is the proportion of CR+PR responders. For Cohort B, the primary analysis will consist of a one-sided exact binomial test of H₀: π =0.30 versus H_a: π >0.30 at level α =0.05.

Additional clinical efficacy endpoints are: (1) changes from baseline to 3 months in the FACT-L Total Score related subscales (physical well-being, social/family well-being, emotional well-being, functional well-being); (2) the 6-minute walk measures (distance, VO2max, shortness of breath scores). All key clinical efficacy outcomes will be considered suitably continuous will be analyzed with an analysis-of-covariance (ANCOVA) approach regressing change from baseline to three months on the baseline value of the respective measure adjusted for baseline tumor volume, age, and sex.

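### The protocol defines its population in two ways, and the eligibility wording admits candidates for curative chemoradiation whom the Section 4.1 design sentence excludes

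*Combined protocol and SAP*

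**What the plan says.** Two definitions of the population stand side by side.

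- **Narrow.** The first sentence of Section 4.1, which covers Phase I and both Phase II cohorts, places the treatment "in patients with malignant airway obstructions that are refractory to curative chemoradiation or, who are not candidates for curative chemoradiation".
- **Broad.** The Cohort A paragraph later in the same section describes "patients with a diagnosis of lung cancer or other malignancies causing airway obstruction or inoperable malignancies not candidates for curative radiotherapy within the airway", and the Cohort B paragraph follows the same pattern. Criterion 4 in Section 5.1 has the same two branches and adds a threshold to the first: lung cancer or "other malignancies causing airway obstruction > 25% requiring bronchoscopic intervention. Or inoperable malignancies not candidates for curative radiotherapy within the airway". The Section 6 table gives airway narrowing as one route and then "Or Cancer is not a candidate for surgery or curative radiation therapy". Section 12 is worded much like Section 6.

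The nearest exclusion in Section 5.2 is "Participants who have had curative radiotherapy to the target tumor within 4 weeks prior to the scheduled I-PDT and/or PDT". The last one is discretionary: "Any condition which in the Investigator's opinion deems the participant an unsuitable candidate to receive I-PDT or PDT".

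On the analysis, Section 12.1.3 says: "The primary analysis will consist of a one-sided exact binomial test". The null for CR+PR at week 12 is 0.05 in Cohort A and 0.30 in Cohort B, each at one-sided 0.05. Section 12.1.6 gives n=18 and n=39.

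**The concern.** Sites enrol by the criteria, not by the design sentence. Up to 32 patients may come from external sites (Section 4.1.4), and Appendix C says that no exceptions to eligibility are granted. An untreated patient with 30% obstruction who needs bronchoscopy and is fit for curative chemoradiation meets criterion 4 as written.

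The primary test has no control arm, so its meaning depends on the null being right for the patients enrolled. Sections 9 and 12 give no rule for anticancer treatment started after I-PDT, and Section 8.1.10 keeps patients on study and goes on collecting response data. A curative candidate could have chemoradiation after I-PDT, respond by week 12 and be counted as an I-PDT responder. A positive result would then be hard to attribute to I-PDT in the population that the design sentence names.

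**Working it through.** **Step 1: does any other text supply the missing condition?**

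- Criterion 2 is a case review for anatomic feasibility only.
- Criterion 3 applies to Cohort B only. It asks whether palliative radiotherapy can be given, not whether curative treatment is possible.
- Criterion 4, obstruction branch: no condition on curative treatment.
- Criterion 4, second branch: inoperable and not a candidate for curative radiotherapy. It has no obstruction threshold and does not mention chemoradiation.
- Exclusion 1 looks back four weeks at curative radiotherapy already given. It does not bar a patient who could still have it.
- Exclusion 10 leaves suitability for I-PDT or PDT to the investigator.

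Nothing closes the gap in the obstruction branch.

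**Step 2: the plan's own figures** (Sections 12.1.3 and 12.1.6). The critical value r is the smallest count with P(Bin(n, p0) ≥ r) ≤ 0.05.

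- Cohort A, n=18, p0=0.05: P(X≥3)=0.058 and P(X≥4)=0.0109, so r=4. Power at 0.29 is 0.812, which matches the stated 0.80.
- Cohort B, n=39, p0=0.30: P(X≥16)=0.094 and P(X≥17)=0.04998, so r=17. Power at 0.50 is 0.832; 80% is reached at 0.491, so the stated 0.50 is slightly conservative.

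The first analysis sentence of Section 12.1.6 attaches the 0.05 null to both cohorts. With n=39 and a null of 0.05, the cut-off would be 5 and 80% power would be reached at about 0.166. The stated 0.50 therefore goes with the 0.30 null.

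**Step 3: effect of curative candidates on the test.** Suppose m of n patients go on to curative treatment and respond at rate q, and the other n−m respond at the null rate p0. Then

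P(success) = Σ_j C(m,j) q^j (1−q)^(m−j) · P(Bin(n−m, p0) ≥ r−j).

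The documents give neither m nor q; both are assumptions. Worked case for Cohort A with m=4, q=0.5: the weights for j=0 to 4 are 0.0625, 0.25, 0.375, 0.25, 0.0625. The tails of Bin(14, 0.05) at 4, 3, 2, 1, 0 are 0.0042, 0.0301, 0.1530, 0.5123, 1. The sum is 0.0003+0.0075+0.0574+0.1281+0.0625 = 0.256.

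Cohort A, P(at least 4 of 18):

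| m | q=0.2 | q=0.3 | q=0.4 | q=0.5 | q=0.6 |
|---|---|---|---|---|---|
| 1 | 0.017 | 0.021 | 0.025 | 0.030 | 0.034 |
| 2 | 0.026 | 0.038 | 0.053 | 0.071 | 0.090 |
| 3 | 0.037 | 0.065 | 0.100 | 0.146 | 0.201 |
| 4 | 0.052 | 0.101 | 0.168 | 0.256 | 0.364 |
| 6 | 0.092 | 0.200 | 0.347 | 0.517 | 0.688 |

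With m=0 the value is 0.011. Cohort A has slack because the exact test is conservative. Cohort B has almost none: with m=8 (8/39 = 21%) and q=0.5, P(at least 17 of 39) = 0.137.

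**The case against.** The strongest reply is that criterion 4 is not the odd one out. The cohort paragraphs of Section 4.1, the Section 6 table and Section 12 all use two branches, and only one introductory sentence is narrower. This stands. A reader might infer that criterion 4 departs from a population that Section 4.1 states consistently. The documents do not support that, because Section 4.1 itself names both branches. A reader might also infer that obstruction above 25% should be required of everyone. That would remove a group that four places in the protocol name.

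Second, the 5% null governs Cohort A only. Cohort B, the larger Phase II cohort, is tested against 30%. This also stands. The documents give no derivation of the 5%, so they do not show that it is wrong for the broader population.

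Third, mild assumptions leave Cohort A under its nominal level: one candidate at 50%, two at 30% or three at 20% all stay below 0.05. This is correct, and the size must be read as illustrative.

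Fourth, later treatment can also confound response in patients with no curative option; Section 8.1.3 expects some participants to be on chemotherapy. So tighter eligibility would not remove all such confounding. It would still remove the patients for whom curative treatment is available.

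None of this removes the conflict between the design sentence and the obstruction branch.

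**Conclusion.** The point holds as an internal inconsistency in eligibility that bears on the primary test. It is not an error in the sample-size arithmetic, which reproduces and does not change with the fix.

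The possible effect runs from negligible to serious. Assuming that everyone else responds at the null rate, the chance of a false success in Cohort A is 0.03 with one curative candidate at 50%. At response rates of 30–60% it is 0.04–0.09 with two candidates, 0.10–0.36 with four and 0.20–0.69 with six. In Cohort B, eight at 50% give 0.14. A reader might take these as forecasts of an inflated error rate. They are not: the documents give no expected number of such patients and no response rate for them.

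Which population is intended is for the sponsor to settle. It should be settled before more patients enter, because analysis cannot fully repair an eligibility problem afterwards.

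**What to change.** Bring Section 4.1 (design sentence and cohort paragraphs), criterion 4, the Section 6 table, Section 12 and the eligibility checklist to one population.

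- **If the design sentence is intended:** add its condition (refractory to, or not a candidate for, curative chemoradiation) to the obstruction branch of criterion 4, and keep the second branch that the cohort definitions name.
- **If the broader population is intended:** amend the design sentence, justify the 5% and 30% nulls for that population, and report candidates for curative treatment separately.

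In either case, correct the sentence in Section 12.1.6 that attaches the 5% null to both cohorts. Apply the change prospectively and state how patients already enrolled in Cohort A are handled; Section 4.1.4 counts eight under its Phase I portion.

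The cost is an amendment to wording and checklist. If the narrower population is kept, accrual will be somewhat slower, which matters in a trial that already allows up to 10 years for 65 patients.

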5.2 Exclusion Criteria

Participants will be excluded from this study for the following:

- 1. Participants who have had curative radiotherapy to the target tumor within 4 weeks prior to the scheduled I-PDT and/or PDT.
- 2. Uncontrolled intercurrent illness including, but not limited to, ongoing or active infection, symptomatic congestive heart failure, unstable angina pectoris, cardiac arrhythmia, or psychiatric illness/social situations that would limit compliance with study requirements.
- 3. Pregnant or nursing female participants.
- 4. Co-existing ophthalmic disease likely to require slit-lamp examination within 14 days following I-PDT and/or PDT treatment.
- 5. Known hypersensitivity/allergy to porphyrin.
- 6. Patients who are not cleared by the anesthesiologist to undergo an advanced bronchoscopy procedure under general anesthesia.
- 7. Patients with target tumor invading into the lumen of the esophagus, confirmed by esophago-gastro-duodenoscopy (EGD) with endoscopic ultrasound.
- 8. Patients diagnosed with porphyria.
- 9. Unwilling or unable to follow protocol requirements.
- 10. Any condition which in the Investigator's opinion deems the participant an unsuitable candidate to receive I-PDT or PDT.

5.2.1 Special Populations

The following special populations are excluded from this study:

- Cognitively impaired adults/adults with impaired decision-making capacity
- Individuals who are not yet adults (infants, children, teenagers)
- Prisoners
- Pregnant women

5.2.2 Inclusion of Women and Minorities

Both men and women and members of all races and ethnic groups are eligible for this study.

6 TREATMENT PLAN

Dosing, Administration and Intervention

The following table summarizes the treatment plan for each study cohort.

Cohort	Participant disease	Treatment	Additional therapy or intervention
Cohort A	Cancer causing airway narrowing.	Participants will be treated with PDT or I- PDT using treatment planning developed by [name] and the treatment	

	Or Cancer is not a candidate for surgery or curative radiation therapy.	planning developed by a company (Simphotek Inc.).	
Cohort B	Cancer causing airway narrowing. Or Cancer is not a candidate for surgery or curative radiation therapy	Participants will be treated with PDT or I- PDT using treatment planning developed by [name].	Participants will receive one treatment of palliative radiotherapy two days before the PDT or I-PDT.

6.1.1 Porfimer Sodium Administration

The intended drug dose of porfimer sodium is 2 mg/kg body weight, administered as a single IV dose 48 ± 4 hours prior to the delivery of the therapeutic light (630 ± 3 nm), as clinically approved.

Drug administration will take place in the Infusion center or the Clinical Sciences Center or in a room that has covered windows to protect the subjects from light exposure that can induce phototoxicity (i.e., direct sun light or visible artificial light that is more than 60 W).

A dose of 2 mg/kg of porfimer sodium will be administered by slow intravenous injection into a vein (3-5 minutes).

6.1.2 EBUS and Light Delivery for I-PDT

Treatment will be administered in the Endoscopy suite at Roswell Park Cancer Institute.

All patients will undergo bronchoscopy under general anesthesia, which is the standard of care procedure for advanced airway management. The patients will be ventilated using laryngeal mask airway (LMA) or endotracheal tube (ETT). The flexible bronchoscope will be used first for airway inspection for obstruction evaluation and, images of the airway obstruction will be taken and saved. Depending on the nature and characteristic of airway obstruction, rigid bronchoscopy may be used during the procedure. When indicated, the airway obstruction will be managed using argon plasma coagulation (APC), laser, electrocautery or mechanical debulking. In cases where the airway obstruction is solely resulting from extrinsically compressing tumor, the airway will be dilated using a controlled radial expansion (CRE) balloon. After establishing airway patency, the EBUS scope will be used to identify extrabronchial tumor (tumor that cannot be visualized in the airway) around the site of airway obstruction. Color-Doppler will be used to demarcate the tumor vasculature.

The pre-treatment plan will follow these steps:

- Obtain high-resolution chest CT scan within 2 weeks ± 1-week prior to planned treatment with EBUS guided I-PDT.
 - A CT scan with 0.625-1.25 mm slice thickness and slice interval of 0.5-1 mm. The CT will be conducted with or without contrast due to known allergy.

- The CT scan will be deidentified to remove all PHI and will only be associated with subject study ID.
- The treating physician will use the deidentified CT scan to mark the target tumor and define the sensitive structure,
- The marked scan will be provided to [name] laboratory for treatment planning.
- The team in [name] laboratory will use computer software (Simpleware) to generate a 3-D reconstruction of the tumor, airway, blood vessels, and all clinically relevant anatomies.
 - When necessary, [name] laboratory will send the 3-D deidentified reconstruction models of the tumor anatomy and adjacent tissues to Simphotek Inc. for meshing. These files with meshes will be returned to [name] laboratory at Roswell Park, for use in the DOSIETM simulations.
- The 3-D model will be presented to the treating physician for review, and to indicate where fibers can be placed, including maximum depth and angles of insertion, relative to the surface of the airway.
- o At [name] laboratory, both DOSIE[™] and COMSOL[™] will be used to generate treatment planning for 630-nm laser. Each plan will use the same number and location of the fiber placement, diffuser length, and intensity (W/cm). The software packages will be used to compute the irradiance and fluence required to administer our target irradiance of ≥ 8.6 mW/cm² in a significant volume of the target tumor. The plans will also suggest the treatment time to deliver ≥45 J/cm² to a significant volume of the target tumor.
- For each plan, the research team will generate a table showing the light delivery options and percent of tumor volume that will receive the minimal and maximal irradiance and fluence for the physician to review.
- The research team will compare the DOSIETM computation with the COMSOLTM. Although both use same input, the differences in the mesh generation and the solvers used in the simulations could impact the resulted irradiance and fluence. The comparison will include percent of tumor that receive ≥ 8.6 mW/cm² and ≥ 45 J/cm², the irradiance and fluence at the margins, the minimum, average, and maximum irradiance and fluence in 100% of the tumor. If there is disagreement (more than 5% difference) we will use COMSOLTM computation.
- The treating physician will review the plan and either approve or request changes.
 - Several iterations (typically 1-3) may be required until the treating physician approves the plan. The review will be in-person or via secured web-based communication (e.g., password protected Microsoft Teams).
 - Once approved, a detailed description of the plan will be provided via secured e-mail.
- The I-PDT procedure will follow the plan as much as possible, taking into consideration patient safety, and treatment time.
 - \circ Our previous studies suggest that fiber placement within ≤ 10 mm from the planned placement will have insignificant impact on the total light irradiance and fluence in the target tumor.

• The difference between the planned and actual placement of the fibers will be recorded (using EBUS imaging and measurements). These data will be used for post analysis, to calculate the actual light distribution by DOSIE[™] and COMSOL[™].

Extrabronchial tumors that are identified by EBUS will be treated with I-PDT. The laser fiber will be inserted into the tumor using the EBUS-TBN. The I-PDT procedure will follow these steps:

- Curvilinear Endobronchial Ultrasound will be used to identify the tumor.
- The EBUS-color Doppler will be used to identify and locate the vasculature inside and adjacent to the tumor.
- EBUS guided transbronchial needle aspiration (Olympus America, Center Valley, PA) will be used to obtain tumor tissue specimen, prior to and after I-PDT. The specimen will be sent to cytology for analysis as per standard of care. Another specimen (tissue obtained prior to light delivery) will be sent to [name] laboratory as described in Section 8.2 below. The electronic health records (I) will be used to review and collect information from the cytology report.
- In this study we will use fiber optics with cylindrical diffuser end that will be obtained from either Pinnacle Biologics Inc. Chicago, IL or Medlight SA, Ecublens, Switzerland. Both fibers will deliver same laser power output that will be checked and confirmed prior to treatment. The preference will be to use the Pinnacle fiber (Micro Diffuser Fiber that is the PB900 model) because it is stiff enough to be placed into the tumor through the 19 G EBUS needle (NA-201SX-4021; Olympus, Tokyo, Japan). This fiber will be provided at no cost to the study.
- In the event that the Pinnacle PB900 will not be available, we will continue to use the Medlight RD250 using a 19 G Cook endoscopic ultrasound needle (Cook Medical LLC, Bloomington, IN). The needle will be shortened to facilitate its use through an Olympus endobronchial ultrasound bronchoscope (Olympus America, Center Valley, PA). The shortened cook endoscopic ultrasound needle will only be used to deliver the PDT laser into the lesion. Shortening will be performed in the Roswell Park Laser Room. Once complete, the needle will be mounted on a specially designed laser fiber holding device.
- The RD250 laser fiber preparation will be performed by inserting the laser fiber into a Progreat® Microsheath Catheter (Terumo Medical Corporation, Somerset, NJ). The microsheath catheter has a clear plastic distal end with Tungsten coil reinforcement. This laser/microsheath catheter will be inserted through the above mentioned shortened endoscopic ultrasound needle. The rationale for this is to provide sufficient stiffness to allow the laser fiber to be held in place within the lesion while the needle is withdrawn from the lesion. The laser power output (from the fiber/catheter end) will be checked and confirmed prior to treatment.
- The laser fiber will be placed within the target tumor under EBUS guidance in one to 10 locations, sequentially. The number and location of the fiber placement will be according to a pre-treatment planning (as much as possible), as the example shown in **Figure 3**.

- If possible (i.e., optional), optical measurement of light transmission and tumor pO2 will be performed before and after I-PDT as described in **section 1.1.13**
- Using either fiber, a 630-nm laser light will be administered with the objective to deliver a minimal irradiance of ≥ 8.6, ≥ 10.8 or ≥ 15.3 mW/cm² to a significant volume of the target tumor, based on Oakley et al. 2019. The treatment time will be adjusted to deliver ≥ 45 J/cm² to a significant volume of the target tumor. The research team will present a table showing the light delivery options and percent of tumor volume that will receive the minimal irradiance and fluence for the physician to review.
- The pre-treatment plan will be presented to the treating physician (the investigator) for review and approval. The investigator will decide how many insertions will be made and where the fiber(s) will be inserted, using clinical judgment and taking into account the patient's safety.
- The I-PDT procedure should be complete within a few hours.
- Airway stenting will be performed after I-PDT, as needed.
 - For cases where airway stenting is indicated to secure the airway, EBUS will be performed before or after airway stenting, as necessary, and the identified portion of the tumor will be evaluated and treated with I-PDT.

At least one tumor will be treated during the I-PDT. The treating physician will determine how many tumors will be treated, taking into account the patient's safety.

6.1.3 Endobronchial tumors that are identified with endoscopy and prior CT or MRI will be treated with I-PDT and/or PDT

- The laser fiber will be placed in the tumor for I-PDT or in the airway for PDT.
- A 630-nm laser light will be administered with the objective to deliver a minimal irradiance of ≥ 8.6, ≥ 10.8 or ≥ 15.3 mW/cm² to a significant volume of the target tumor, based on Oakley et al. 2020. (41) The treatment time will be adjusted to deliver ≥ 45 J/cm² to a significant volume of the target tumor. The research team will present a table showing the light delivery options and percent of tumor volume that will receive the minimal irradiance and fluence for the physician to review.
- The pre-treatment plan will be presented to the treating physician (the investigator) for review and approval. The investigator will decide how many insertions or placements will be made and where the fiber(s) will be positioned, using clinical judgment and taking into account the patient's safety.
- The I-PDT and/or PDT procedure/s should be complete within few hours.
- Airway stenting will be performed after I-PDT and/or PDT, as needed.
 - For cases where airway stenting is indicated to secure the airway, EBUS will be performed before or after airway stenting, as necessary, and the identified portion of the tumor will be evaluated and treated with I-PDT and/or PDT.

